## **3. Confidentiality**

How will confidentiality of data be maintained? Check all that apply.

- Paper-based records will be kept in a secure location and only be accessible to personnel involved in the study.
- Computer-based files will only be made available to personnel involved in the study through the use of access privileges and passwords.
- Prior to access to any study-related information, personnel will be required to sign statements agreeing to protect the security and confidentiality of identifiable information.
- Whenever feasible, identifiers will be removed from study-related information.

  

- A Certificate of Confidentiality will be obtained, because the research could place the subject at risk of criminal or civil liability or cause damage to the subject's financial standing, employability, or liability.
- A waiver of documentation of consent is being requested, because the only link between the subject and the study would be the consent document and the primary risk is a breach of confidentiality. (This is not an option for FDA-regulated research.)
- Precautions are in place to ensure the data is secure by using passwords and encryption, because the research involves web-based surveys.
- Audio and/or video recordings will be transcribed and then destroyed to eliminate audible identification of subjects.
- Other (specify): \_\_\_\_\_

Subject confidentiality will be maintained by keeping records in a secure location. Most of the information will take the form of computer files; these will be de-identified by using a coding process under which subjects are identified by an assigned subject number and the date of the testing. Subject names, ages and ethnicity will be recorded only in a secure, password protected computer location. Signed consent forms and HIPAA forms will be maintained in a secure file at least until the project is terminated. In tasks assessing language production, subjects' responses will be recorded in a digital fashion for later analysis. The digital files will be destroyed after the experiment is completed. In tasks assessing language production, subjects' responses will be recorded in a digital fashion for later analysis. The digital files will be destroyed after the experiment is completed. In order to determine if a subject should be disqualified by virtue of neurologic or psychiatric issues or is consuming a medication that may alter brain membrane potentials, potential subjects will be asked if they have a history of any of the following: seizures, stroke, episodes of loss of consciousness, or psychiatric illness requiring treatment. They will also be asked to indicate if they

are taking medications for seizures, bipolar disorder, ADHD, OCD, schizophrenia or psychosis. PHI that is to be collected includes subject names, addresses, contact information and Social Security Number. The latter is necessary for subject payment. This information will be stored in a protected computerized subject database. PHI will not be disclosed to anyone not listed in the IRB-approved list of personnel.

#### **4. Subject Privacy/Protected Health Information**

The potential subjects for this study will be drawn from the practices of the cognitive neurologists at the Univ. of Penn, 3 of whom are participating in the study ([name], [name], [name]). Our colleagues ([name], [name], [name]) know of the study and have indicated that they would be happy to refer appropriate subjects. Potential subjects will be contacted initially by their treating physician; after learning of the study and indicating that they want to hear more about it, they will be contacted by study personnel. There is a chance that subjects will contact us; the world of Primary Progressive Aphasia is pretty small; the disorder is rare and there are support groups and links between patients. It is possible that someone seen at another institution will hear of the study and contact us to see if they are eligible. Assuming they met Inclusion/Exclusion criteria, these subjects would be included in the study. Patients referred from clinicians other than Drs. [name], [name] or [name] will be subject to an initial screening visit prior to enrollment to determine eligibility and diagnosis confirmation.

#### **5. Tissue Specimens**

Not applicable.

#### **6. Genetic Testing**

Not applicable.

### **RISK/BENEFIT ASSESSMENT**

#### **1. Potential Study Risks**

Risks from tDCS in the normal population appear to be minor. The most common adverse effect in a published review of our experience at Penn (Kessler et al., 2012) was itching and mild burning at the site of stimulation (that is, under the electrode). We have not observed significant adverse effects in more than 500 testing sessions and, to the best of our knowledge, no significant adverse effects have been reported elsewhere. Participants receiving sham stimulation can sometimes

experience side effects similar to those experienced during real tDCS stimulation. This is because sham stimulation involves approximately 30 seconds of real stimulation before the machine shuts off. tDCS is currently regarded by the IRB as a minimal risk procedure in normal subjects. tDCS has been employed safely in patients with a variety of neurologic disorders including stroke and degenerative diseases (references cited previously). We are aware of one abstract (Wang et al., 2013) reporting tDCS as a treatment in a single subject with PPA in which the procedure appears to have been well-tolerated and possibly efficacious (the data are very limited). Overall, the potential risks appear to be modest. The risks associated with tDCS are not altered if the stimulation is conducted at a patient's home or if it is conducted in the lab. Similarly, HD-tDCS is safe and equally well-tolerated as conventional tDCS. Consistent with the favorable safety profile of tDCS, protocol #814366 was approved by the IRB of the University of Pennsylvania and HD-tDCS was deemed a minimal risk technique.

### ***2.1 Potential Study Benefits of tDCS-Only Study and tDCS with svPPA sub-study***

The study is being performed to determine if tDCS improves subjects' language performance. The potential benefit of the study to the subjects, therefore, is that they will improve with respect to language function. The study will also be of benefit to the community of physicians and clinicians attempting to treat PPA.

### ***2.2 Potential Study Benefits of HD-tDCS+CILT Sub-study***

The study is being performed to determine if HD-tDCS in combination with CILT improves subjects' language performance. The potential benefit of the study to the subjects, therefore, is that they will improve with respect to language function. This may occur during CILT+sham, CILT+HD-tDCS, or both. The study will also be of benefit to the community of physicians and clinicians attempting to treat PPA.

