**PROTOCOL ABSTRACT**

The purpose of this study is to treat the language impairment of subjects with Primary Progressive Aphasia using transcranial direct current stimulation (tDCS) and high definition transcranial direct current stimulation (HD-tDCS). PPA is a slowly progressive impairment in language that may be observed in patients with neurodegenerative conditions such as Fronto-temporal dementia or, less commonly, Alzheimer's Disease. tDCS is a form of non-invasive brain stimulation in which very small current (here, 1.5 mA) is applied to the scalp. tDCS will be administered in ten 20 minute sessions over the course of two weeks. Language function will be assessed before, after 1 week of treatment, after 2 weeks of treatment and at 6 and 12 weeks after completion of tDCS. In a sub-study under this protocol, we will pair HD-tDCS with Constraint-Induced Language Therapy (CILT), which preliminary evidence has shown may be a useful speech therapy for individuals with PPA. In this sub-study, we will investigate whether HD-tDCS can enhance the potential benefits of speech therapy (usually very modest in PPA).

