### **1.2 HD-tDCS+CILT Sub-study Objectives**

The objective of the HD-tDCS+CILT sub-study is to improve language function in patients with Primary Progressive Aphasia using a combination of HD-tDCS and a form of intensive speech therapy called Constraint-Induced Language Therapy. The HD-tDCS+CILT sub-study shares many of the design features of the tDCS-Only study in 1.1, therefore, we will include additional information about HD-tDCS+CILT in its own section where relevant to help delineate the differences between these two studies. Any sections that do not include a HD-tDCS+CILT sub-section apply identically to both studies.

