### **1.3 tDCS for svPPA Sub-study Objectives**

The objective of the tDCS with svPPA sub-study is to improve language function in patients with semantic variant Primary Progressive Aphasia using a combination of tDCS and speech therapy.

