Half of subjects will undergo 10 sessions of sham stimulation first and will then undergo 10 sessions of real tDCS stimulation. Half of subjects will undergo 10 sessions of real tDCS stimulation first and will then undergo 10 sessions of sham stimulation. A complete language assessment will be performed before stimulation sessions, after the 10th stimulation session, and 12 weeks and 6 months ( $\pm$  1 week) after the completion of stimulation sessions. Real tDCS stimulation will be administered using the Soterix 1x1 using a current of 2 mA. The cathodal current will be split across two electrodes (5cm^2) positioned over the left and right temporal regions respectively. The anodal electrode (5x7cm) will be placed over the forehead. During sham stimulation, a 2 mA current will be delivered for approximately 10 seconds at the beginning of the sham condition before being extinguished over the course of seconds. After the first 10 minutes of stimulation, in both real and sham conditions, participants will begin the behavioral treatment, which will continue for 45 minutes; therefore there will be 20 minutes of concurrent tDCS and behavioral therapy.

Prior to initiating treatment, we will craft an individualized training lexicon for each patient. This training vocabulary contains familiar people, household items, foods, activities, cloths, and hygiene implements. Target words are represented by photographs of the patient's own items. We will employ several item-level controls to examine treatment generalization. The first will test the impact of personal familiarity by asking patients to name and generate features for canonical rather than personal photographs. The second condition will evaluate within-category generalization by asking patients to name and generate features for their own untrained items. The final item-level comparison will examine generalization of naming accuracy to untrained

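### The HD-tDCS+CILT and svPPA aims are worded as effects of stimulation plus therapy, but therapy accompanies both real and sham stimulation, so the randomized comparison identifies only what stimulation adds

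*Combined protocol and SAP*

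**What the plan says.** For HD-tDCS+CILT, Objectives 1.2 aims at better language "using a combination of HD-tDCS and a form of intensive speech therapy called Constraint-Induced Language Therapy", and Risk/Benefit 2.2 gives the purpose as "The study is being performed to determine if HD-tDCS in combination with CILT improves subjects' language performance". The Protocol Abstract puts a different question for the same sub-study: "we will investigate whether HD-tDCS can enhance the potential benefits of speech therapy".

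For svPPA, Objectives 1.3 aims at better language in "semantic variant Primary Progressive Aphasia using a combination of tDCS and speech therapy". Risk/Benefit 2.1, whose heading covers the tDCS-Only study and the svPPA sub-study, says: "The study is being performed to determine if tDCS improves subjects' language performance".

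Therapy is common to both conditions. Study Procedures 1.2 runs a CILT session after set-up for either HD-tDCS or sham, and Risk/Benefit 2.2 expects that gains may appear with sham as well as with real stimulation. For svPPA, Study Procedures 1.3 says that "in both real and sham conditions, participants will begin the behavioral treatment".

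The Statistical Analysis section plans within-subject tests of change from baseline to the post-therapy visits. Primary Outcome Variable(s) plans a comparison of performance before and after tDCS. Neither names a contrast of real with sham.

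**The concern.** Whether stimulation adds to therapy and whether stimulation plus therapy improves language are different questions. A sham-controlled crossover with therapy in every block addresses the first. The second needs something to stand for the course of language without therapy, and neither sub-study has a control of that kind.

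The wording matters because of the analysis attached to it. If the aim is that the combination improves language and the test is change from baseline, a gain within a block can be taken as success even when real and sham blocks gain equally. Such a gain has other possible sources. HD-tDCS+CILT participants repeat the assessments at nine visits (Study Procedures 1.2), so practice is plausible, and the same section concedes that performance varies considerably in this disease without any intervention. The only evidence on CILT in PPA that the Background describes is a study of two individuals, which gives no usable external value to subtract.

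**Working it through.** The plan states no model, effect size or power for this point, so there is no figure to reproduce. The question is which effects the design can identify. The additive models below are mine.

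**Inputs.** Two sequences, sham-first and real-first, each taking half of the participants; two blocks per participant; therapy in all four sequence-by-block cells (Study Procedures 1.2 and 1.3); 2-week blocks; 12 weeks without treatment before the crossover (both Study Design sections numbered 2.2).

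**1. Expected change within a block.** Let *n* be natural course, practice and placebo response together, *p* the shift in the second block, *s* the effect of stimulation given with this therapy, and *t* the effect of therapy.

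| Cell | n | p | s | t |
|---|---|---|---|---|
| Sham-first, block 1 | 1 | 0 | 0 | 1 |
| Sham-first, block 2 | 1 | 1 | 1 | 1 |
| Real-first, block 1 | 1 | 0 | 1 | 1 |
| Real-first, block 2 | 1 | 1 | 0 | 1 |

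The columns for *n* and *t* are identical, so the rank is 3 of 4.

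- Stimulation: real minus sham within a participant is *s* + *p* for sham-first and *s* − *p* for real-first. The average is [(*s* + *p*) + (*s* − *p*)]/2 = *s*, which is estimable.
- Therapy and combination: the data give only *n* + *t* and *n* + *s* + *t*. Neither *t* nor *s* + *t* can be recovered without knowing *n*.

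This model has no carry-over term. Carry-over of first-block stimulation would disturb the within-subject estimate of *s*, but it would not free *t*.

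**2. Can the treatment-free weeks serve as the control?** Let *b* be the natural slope per week.

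- With a constant slope, no decay of the treatment effects, and no separate term for practice or placebo response, a sham block changes by 2*b* + *t* and the next 12 weeks by 12*b*. Then *t* = (sham-block change) − (2/12)(12-week change). The rank is 3 of 3 and *t* is estimable.
- Now let the therapy and stimulation effects fade, adding a term for each to the 12-week change. The rank is 4 of 5. Raising *b* by 1, lowering *t* by 2 and lowering the therapy-decay term by 12 leaves every expected value unchanged: 2 − 2 = 0 over the block and 12 − 12 = 0 over the interval. So *t* and *s* + *t* are again not estimable, while *s* still is.

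Every treatment-free interval of this kind follows therapy, so the no-decay assumption cannot be avoided. Before therapy, HD-tDCS+CILT has baseline sessions on separate days but no planned untreated control interval.

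**3. Confirming the cause.** Adding one hypothetical cell with neither therapy nor stimulation (row 1, 0, 0, 0) to the table raises the rank to 4 of 4, and *s*, *t* and *s* + *t* all become estimable. The missing no-therapy cell is what limits the design.

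**4. svPPA item comparisons.** Study Procedures 1.3 also tests the patient's own untrained items and untrained Philadelphia Naming Test exemplars. This gives a partial, item-level comparison of training with practice and natural course. It is presented as a test of generalization. The randomization mentioned there concerns the order in which items are trained; no random assignment of items to trained or untrained is described. It therefore does not give the effect of the combination on overall language.

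**The case against.** The strongest reply is that the design is sound and only some sentences are loose. Sham plus therapy against real plus therapy is a coherent add-on trial. Objectives 1.2 and 1.3 express a hope of improving language, in the same form as Objectives 1.1, and state no hypothesis. Risk/Benefit 2.2 sits in a section on benefits, and its phrase can be read as stimulation given alongside CILT. The Abstract and Risk/Benefit 2.1 already ask questions that the design can answer.

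Much of this stands. The fault is an inconsistently stated aim joined to an analysis that does not resolve it, and the add-on comparison remains valid. Three stronger readings are not supported:

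- A reader might infer that participants have no untreated time. They do: 12 weeks before the crossover. These weeks fail as a control because they follow therapy.
- A reader might infer that nothing at all can be learned about training in svPPA. The untrained items give partial information.
- A reader might infer that the sponsor intends to report a rise in both blocks as success. No passage says so; the plan merely does not exclude it.

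The Background questions on how well CILT works and for how long are background, not stated endpoints, so leaving them unanswered is not a failure of the plan.

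What the reply does not remove is that Risk/Benefit 2.2 says what the study is to determine, and the Statistical Analysis section names no contrast that would limit the answer to the effect of stimulation.

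**Conclusion.** The point holds in this form: the HD-tDCS+CILT and svPPA aims are stated inconsistently, and the randomized comparison supports only the stimulation question. Of stimulation, therapy and their sum, one of three is estimable (rank 3 of 4). A larger sample would not change this.

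The result assumes an additive model with therapy delivered in both blocks, as the procedures describe. Identifying the therapy effect from the treatment-free weeks would need a constant natural slope, no fading of the treatment effects and no separate practice or placebo effect, none of which the documents establish. The trial is not invalid for the add-on question; what should be corrected is the stated aim and the analysis that would be read against it.

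**What to change.** 1. Reword Objectives 1.2 and 1.3 and Risk/Benefit 2.2 to agree with the Abstract and Risk/Benefit 2.1: does active stimulation, compared with sham, add to the language outcome of the same therapy?
2. In Statistical Analysis, and to match in Primary Outcome Variable(s), name the within-subject real-versus-sham contrast of change from baseline as the efficacy analysis. Rewording the objectives alone would leave the before-and-after tests in place.
3. State that change within a block is descriptive and supports no efficacy conclusion on CILT, on the semantic training or on the combination.

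The cost is protocol wording and a narrower claim.

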### ***3. Alternatives to Participation***

The alternative to participation is to not participate. Subjects' participation in other research projects will not be influenced by a decision to not participate in this project.

### ***4. Data and Safety Monitoring***

The PI will monitor the progress of the study, including safeguarding data and monitoring for

adverse effects.

**5. Management of Information for Multi-center Research where a Penn Investigator is the Lead Investigator of a multi- center study, or Penn is the lead site in a multi-site study.**

Not applicable.

**6. Risk/Benefit Assessment**

The risks as well as the potential benefit of the study are modest. tDCS has been delivered to subjects with primary degenerative diseases of the brain in multiple studies without adverse effects. The benefits, however, are also expected to be modest. The treatment may improve language function but in the setting of a primary degenerative condition, the benefit is likely to be modest. There is no reason to believe that the treatment will modify the underlying course of the disease.

**SUBJECT COMPENSATION**

Subjects will be compensated at a rate of \$25/hour for their time while participating in the study.

Typically, participants are compensated via mailed check, however, we have received approval from the department to use the GreenPhire clin-card system. The GreenPhire clin-card is a reloadable debit card. These can be used to provide payment for participation in research studies, as well as payment for transportation costs related to participation in research. Each subject is given a GreenPhire card and, once the system is set up, subjects can be paid immediately following each session, including for any transportation costs. Subjects can then use the card like a credit or debit card at various merchants, can withdrawal money at any ATM (though there may be fees associated with this option), or can withdrawal the balance of the card at any bank (no fees associated with this option). This method of payment is only an option and is not a requirement. Participants and the research staff will together make the decision about which payment option is best.

**INFORMED CONSENT**

**1. Consent Process**

Consent will be obtained by Drs. [name], [name] or [name] or one of their research associates. Subjects who are not judged to be competent to give informed consent by the investigators will have their Legally Authorized Representative (LAR) give consent on their behalf. In these cases,

the LAR will sign the ICF/HIPAA in the appropriately labeled space.

## **2. Waiver of Authorization**

Not applicable.

## **RESOURCES NECESSARY FOR HUMAN RESEARCH PROTECTION**

Research staff related to this project include the PI, Co-investigators (Drs. [name] and [name]) and other personnel. All research staff will undergo training on research practices involving human subjects, including the protection of subject confidentiality, and will maintain current certification in patient oriented research. Moreover, all investigators will have experience administering tDCS.

During the first stimulation session, participants will come to the lab here at the University of Pennsylvania and a physician will be on call within 5 minutes of the testing room. As long as the subject does not experience any adverse events during that first stimulation session and the research staff have no reservations, then in all subsequent stimulation sessions, whether conducted in the patient's home or in the laboratory here at the University of Pennsylvania, one of the physicians associated with the study will respond to any concerns within 24 hours. The trained personnel administering stimulation will look for any evidence of discomfort in the participant and will verbally inquire about any discomfort. The investigator or trained personnel will also observe and monitor the equipment. In the unlikely event that either the subject or the person administering tDCS has significant concerns and the PI cannot be immediately contacted, the subject would be escorted to the Emergency Room.

Staff will also be trained on the correct administration of the specific psychometric tests of language and cognition employed in proposed research. Subject Recruitment: Patients with PPA will be recruited from two sources: 1) the clinical practices of Drs. [name], [name], and [name], 2) [name] IRB-approved protocol entitled "Neural Basis for Frontotemporal Degeneration" (#298201). Potential subjects identified in the clinical practices of Drs. [name], [name] and [name] will be contacted by their treating physician. Potential subjects involved in research with [name] and his team will be contacted by the research staff with whom they interact in the on-going research project.

Facilities: Subjects will be stimulated and tested in HUP or Perelman School of Medicine buildings. Depending on the availability of rooms, three testing sites may be employed: Neurology out-patient

offices in the Perelman Center, Neurology out-patient offices on Ravdin 2 or the laboratory of [name] (Gibson 3). The HD-tDCS apparatus is portable and no special equipment is required. Additionally, if it is convenient for the patient, we may conduct stimulation sessions in the patient's home. In order to be eligible for home visits, patients must live within 40 miles, or approximately one hours, of the University of Pennsylvania. Ultimately, the discretion for eligibility and scheduling will be up to the researcher and the Principal Investigator, in order to best effectively and efficiently manage the lab's resources. If patients do qualify for home visits, they will come to the lab for their first stimulation session. If the patient does not experience any adverse events during that stimulation session and if the other requirements are met, then all subsequent stimulation sessions would be conducted in the patient's home. Again, we would like to stress that this is only an option, not a requirement, which patients may choose if it is more convenient for them. Patient visits not requiring the use of tDCS may be conducted at the patient's home if this situation proves to be more convenient for the patient.

**Device:** Recently, Magstim, the largest manufacturer of TMS equipment in the world, has developed a tDCS apparatus, the Magstim Eldith 1 Channel DC Stimulator Plus. The unit is powered by rechargeable batteries and includes a microprocessor controlled unipolar and bipolar constant source for anodal and cathodal stimulation. Both tDCS and HD-tDCS will be administered using Magstim Eldith DC stimulators. A Soterix 4x1 HD-tDCS adaptor will be used to convert the traditional tDCS unit to allow for HD stimulation. We note that these apparatuses are currently being employed in an IRB approved protocol (#809185 and #814366) in which more than 200 tDCS sessions have been conducted without significant adverse effects. The unit is not FDA approved for any clinical purposes. The tDCS and HD-tDCS units will be used in a locked laboratory in HUP in which the lab's TMS apparatus is currently situated. Only the PI and other members of his research team have keys to this laboratory. When not in use, the unit will be enclosed in a special, dedicated storage container that will be marked with a statement that the enclosed unit is not to be used for clinical purposes. During these times the unit will be housed in the PIs personal space located in the University of Pennsylvania School of Medicine and stored in a locked cabinet to which only the PI and his staff have access. Additionally, the unit itself will be clearly marked with a statement indicating that it is an investigational instrument only.

